8.3.4.1. Chemistry, Serology, Hematology, and Urinalysis

A panel of standard serum chemistries, hematology, and urinalysis tests will be analyzed at times shown in [Table 3](#). A list of required analytes is provided in [Table 10](#). All serum chemistries will be performed from blood samples collected without respect to food intake (ie, nonfasting).

[figure not shown]
Assessments will be performed at the screening visit to rule out HIV infection. Serology tests should be performed early in the screening process due to the length of time needed to obtain the results. Additional tests may be performed if clinically needed.

[figure not shown]
8.3.4.2. Pregnancy Testing

[figure not shown]
A serum pregnancy test will be required for all WOCBP during screening. Urine pregnancy tests will be performed at other specified visits outlined in [Table 3](#). If a urine pregnancy test is positive, the results should be confirmed with a serum pregnancy test.

If the serum pregnancy test is negative after a urine test was positive, the investigator will assess the potential benefit/risk to the participant and determine whether it is in the participant's best interest to resume study drug and continue participation in the study.

If a pregnancy is confirmed by a serum pregnancy test, see Section [9.7](#) for reporting requirements.

8.6. Unscheduled Visits

Unscheduled study visits may occur at any time as medically warranted. Any assessments performed at those visits should be recorded in the eCRF.

If the participant develops new areas of AD, documentation of the new BSA may occur at an unscheduled visit if appropriate.

8.7. End of Treatment and/or Early Termination

If a decision is made that the participant will permanently discontinue study drug, then the ET visit should be conducted. If the ET visit coincides with a regular study visit, the ET evaluations will supersede those of that scheduled visit, and the data should be entered in the ET visit in the eCRF. If this decision does not coincide with a regular visit, reasonable efforts should be made to have the participant return to the site to have the ET procedures completed. The participant should be encouraged to return for the follow-up visit.

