8.2.2.2. Abbreviated 9-Item Treatment Satisfaction Questionnaire for Medication

On Day 29 (or ET as applicable), participants will be asked to complete the TSQM-9. The TSQM-9 is a 9-item measure that assesses the most common dimensions participants use to evaluate their medication (ie, global satisfaction, effectiveness, and convenience). The results for each scale are presented from 0 to 100, where higher scores represent better satisfaction. The questionnaire is provided separately from the protocol.

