5.4 Windowing Conventions

No windowing conventions apply for this study.

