5.7 Handling of Retests, Unscheduled Visits, and Early Termination Data

When retests measurements are done, the retest measurement will be considered for the summary analysis. All data from retest visits will be listed.

Unscheduled measurements will not be summarized in by-visit summary tables or figures. However, they will be included in shift summary tables. All data from unscheduled visits will be listed.

Early Termination visit assessments will be summarized as a separate visit in by-visit outputs. All data from early termination visits will be listed.

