6.2 Handling of Dropouts or Missing data

No imputation will be made for efficacy data. See [Appendix 2](#) for handling of completely or partially missing dates for prior and concomitant medications and adverse events.

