12.2.4 Investigator's Global Assessment

The Investigator's Global Assessment (IGA) of the current state of the disease is a 5-point morphological assessment of overall disease severity.

The IGA will be analyzed as follow:

- Change from baseline in IGA at Day 8, Day 15, and Day 29.

The Investigator's Global Assessment-Treatment Success (IGA-TS) is defined as an IGA score of 0 or 1 with at least a 2-grade reduction from baseline. The IGA-TS will be analyzed as follow:

	STATISTICAL ANALYSIS PLAN, Version Final v1.0
Protocol Number: INCB 18424-901	Sponsor: Incyte Corporation
Study Title: An Open-Label, Single-Arm Study to Evaluate the Effect of Ruxolitinib 1.5% Cream on Itch in Adult Participants With Atopic Dermatitis (SCRATCH-AD)	

- Proportion of participants achieving the IGA-TS (score of 0 or 1 in IGA with at least a 2-grade reduction from baseline) at Day 8, Day 15, and Day 29.

[figure not shown]

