12.2.5 Secondary Endpoints Analysis

Descriptive statistics will be presented for all secondary efficacy endpoints, by visit and timepoint (if applicable). The change from baseline and percent change from baseline in PP-NRS, mPP-NRS and IGA, and proportion endpoints for PP-NRS, mPP-NRS, and IGA-TS, will be analyzed descriptively at each visit. The 95% CI will be provided for the mean change, percent change and the proportions (using the Clopper-Pearson method). For proportion endpoints, percentages will be based on the number of participants with a response at the specified visit and timepoint.

The proportion of participants achieving an IGA score of 0 or 1 and associated 95% CI (using the Clopper-Pearson method) will also be reported descriptively.

The time to MCID will be analyzed using Kaplan Meier estimation for PP-NRS and mPP-NRS. A participant will be considered censored if he has not met the event of interest at the end of the study or if the participant is lost to follow up at last observation. Those participants will be censored at their last available mPP-NRS or PP-NRS assessment date or time. Survival curves will also be presented.

A line graph presenting the value and a line graph presenting the change from baseline in mPP-NRS over time will be produced. The value and change from baseline in PP-NRS over time and value and change from baseline in IGA will be presented similarly.

	STATISTICAL ANALYSIS PLAN, Version Final v1.0
Protocol Number: INCB 18424-901	Sponsor: Incyte Corporation
Study Title: An Open-Label, Single-Arm Study to Evaluate the Effect of Ruxolitinib 1.5% Cream on Itch in Adult Participants With Atopic Dermatitis (SCRATCH-AD)	

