12.4 Other Analyses

12.4.1 Abbreviated 9-Item Treatment Satisfaction Questionnaire for Medication

The Abbreviated 9-Item Treatment Satisfaction Questionnaire for Medication (TSQM-9) is a 9-item measure that assesses the most common dimensions participants use to evaluate their medication (ie, global satisfaction, effectiveness, and convenience). The results for each scale (global satisfaction, effectiveness, and convenience) are presented from 0 to 100, where higher scores represent better satisfaction. Scoring method for each scale is presented in [Appendix 3](#).

TSQM-9 data for each scale will be summarized separately by visit using descriptive statistics. All TSQM-9 data will be listed.

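### Assessments taken on schedule at Day 8 or Day 15 drop out of that visit's IGA, EASI and BSA results when the participant stops study drug at that visit

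*Protocol*

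**What the plan says.** Five provisions act together.

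- **Protocol 8.7** requires an ET visit once it is decided that study drug will be stopped permanently. If that visit falls together with a regular one, "the ET evaluations will supersede those of that scheduled visit, and the data should be entered in the ET visit in the eCRF".
- **SAP 5.7**: "Early Termination visit assessments will be summarized as a separate visit in by-visit outputs". It adds that all ET data are listed.
- **SAP 5.4**: "No windowing conventions apply for this study".
- **SAP 6.2**: "No imputation will be made for efficacy data".
- **SAP 12.2.5**, on the proportion endpoints: "percentages will be based on the number of participants with a response at the specified visit and timepoint".

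Protocol Table 3 (Schedule of Activities) places IGA at Day 8, Day 15, Day 29 and ET. It places EASI and total BSA at Day 15, Day 29 and ET. At Day 8 and Day 15 these are done before the morning application. SAP 12.2.4 defines IGA change and IGA-TS at Day 8, Day 15 and Day 29.

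**The concern.** Someone who comes to Day 15 on time, is assessed before the morning application and stops there has had the same treatment interval as those who carry on. The IGA is a Day 15 IGA in every respect except the eCRF page on which it is entered. Under the rules as written it cannot enter the Day 15 result, although the secondary endpoints are defined at that day.

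This differs from ordinary missing data. The value exists, was taken at the planned time, and is kept out of the row by its label, so restoring it needs no missing-data assumption. The exclusion is also selective, because it applies only to people who stop. One listed ground for permanent discontinuation in Protocol 6.5.2 is worsening of the dermatitis that needs a prohibited medication, which is the kind of change that IGA, EASI and BSA record. The ET row does not replace the missing entries, since it pools stops from any study day and has no single time point.

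At stake is the accuracy of the Day 8 and Day 15 summaries. The study has one arm and makes no formal comparisons (SAP 5.6), so these descriptive summaries are themselves the result.

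**Working it through.** **1. Following one record through the rules.** Take a participant who attends Day 15 and stops study drug permanently at that visit.

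- Protocol 8.7: IGA, EASI and total BSA are entered as ET, and no Day 15 record remains.
- SAP 5.7: the ET record goes to an ET row.
- SAP 5.4: nothing moves it to Day 15.
- SAP 6.2: nothing fills the Day 15 gap.
- SAP 12.2.5: with no Day 15 response, the participant leaves the denominator as well as the numerator of the Day 15 proportions.

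No other section of either document reverses this. At Day 8 the same applies to the IGA results only, because EASI and total BSA are not scheduled then.

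**2. The plan's own figures.** The documents give no discontinuation rate, IGA response rate or IGA standard deviation. Their one sample-size calculation (Protocol 10.1) reproduces: (1.96 × 1.64 / 0.57)² = 31.8, rounded up to 32; 32 / 0.9 = 35.6, rounded up to 36. It concerns the Day 2 PP-NRS and has no bearing here. What follows is illustration.

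**3. Mean IGA change.** The planned total of 48 comes from Protocol 10.1. Assumptions: all 48 attend, k stop at the visit with a change of +1, and the other 48 − k average −1.00. The planned row shows −1.00 whatever k is. The mean of all observed values is [(48 − k)(−1) + k(+1)] / 48.

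| k | Calculation | Mean, all observed | Shift from −1.00 |
|---|---|---|---|
| 1 | (−47 + 1)/48 | −0.958 | 0.042 |
| 2 | (−46 + 2)/48 | −0.917 | 0.083 |
| 3 | (−45 + 3)/48 | −0.875 | 0.125 |

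For scale, with an assumed SD of 0.7 to 1.0 for IGA change, the 95% half-width at n = 48 is 2.012 × SD / √48, or 0.20 to 0.29.

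**4. IGA-TS.** Assume x responders among 48 attending, and k non-responders who stop at the visit. The observed proportion is x/48; the reported one is x/(48 − k).

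| x | Observed | k = 1 | k = 2 | k = 3 |
|---|---|---|---|---|
| 12 | 12/48 = 25.0% | 12/47 = 25.5% | 12/46 = 26.1% | 12/45 = 26.7% |
| 24 | 24/48 = 50.0% | 24/47 = 51.1% | 24/46 = 52.2% | 24/45 = 53.3% |

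The Clopper-Pearson 95% interval for 12/48 is 13.6% to 39.6%.

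This size does not carry over directly to EASI-75. SAP 12.4.3 states no denominator for it, and the default in SAP Appendix 1 is the whole analysis population. Under that default, losing a non-responder's record would not change the percentage.

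**The case against.** **Nothing is discarded.** The ET values are summarized in their own row and listed, so a careful reader can find them. That stands: they are absent from the nominal-visit row, not from the report.

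**Direction is not established.** Worsening dermatitis is one route to stopping. Protocol 7.1.1 and 7.2 give others, such as pregnancy, withdrawn consent, noncompliance and administrative reasons. With no rate or mix of reasons in the documents, a more favourable by-visit result is conditional on those who stop doing worse. That also stands.

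**The effect is probably small.** Even the 0.125 shift lies within the assumed confidence half-width. This limits the importance of the point. It does not justify leaving observed on-schedule values out.

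**A separate ET row is sensible for off-schedule stops.** An ET visit held between scheduled visits may come after drug was stopped or another therapy begun. Moving every ET record within ±2 days into a scheduled visit would be a decision about post-discontinuation data. This is right, and it confines the remedy to visits that actually coincide.

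Three stronger readings are tempting, and the documents do not support them.

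- *The primary result is biased.* PP-NRS is captured daily in the eDiary (Protocol 8.1.4), and mPP-NRS is assessed on Day 1 only (Protocol 8.2.2.1.2). The relabelling touches neither.
- *Day 29 and laboratory results are affected in the same way.* The last application is the evening before the Day 29 visit, so a participant still on treatment then has nothing left to discontinue. Only an earlier stop whose ET visit happens to fall at Day 29 is caught. Laboratory tests are not scheduled at Day 8 or Day 15, so they depend wholly on that rare case.
- *The treatment satisfaction questionnaire suffers the same fault.* Protocol 8.2.2.2 says "On Day 29 (or ET as applicable), participants will be asked to complete the TSQM-9", and SAP 12.4.1 says "TSQM-9 data for each scale will be summarized separately by visit using descriptive statistics". A questionnaire from someone who stopped between visits was never an on-schedule Day 29 value. Separate rows keep different treatment durations apart, and pooling them is a presentation preference.

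**Conclusion.** The point holds for participants who permanently stop study drug at a scheduled Day 8 or Day 15 visit. Their on-schedule values leave that visit's results for IGA change, IGA-TS and IGA 0/1, and at Day 15 also for EASI, EASI-75 and total BSA.

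Under the assumptions shown, 1 to 3 such participants out of 48 would make the mean IGA change look better by 0.04 to 0.125 grade, and IGA-TS by 0.5 to 3.3 percentage points. If nobody stops at those visits there is no effect. If those who stop do as well as the rest, the results are not flattered. This is a correction worth making to secondary and other by-visit summaries. It does not call the primary analysis into question.

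**What to change.** Add one rule to SAP 5.7, with a matching exception in SAP 5.4: when the ET visit coincides with a scheduled visit under Protocol 8.7, the assessments scheduled for that visit are also included in its by-visit summaries and proportions, and are still shown and listed under ET. Limiting the rule to coinciding visits and to assessments planned for that visit leaves off-schedule ET records where they are. It also keeps an EASI or BSA taken at a Day 8 stop from creating a Day 8 row that was never planned.

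The cost is one visit-mapping step in the analysis datasets, with no new data, no imputation and no change to study conduct. A coinciding record will appear in two rows, so the tables need a footnote saying so. By-visit results may become slightly less favourable.

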8.8. Follow-Up

8.8.1. Safety Follow-Up

The safety follow-up period is the interval between the Day 29 visit and the scheduled follow-up visit and should occur 15 (\pm 2) days after the last application of study drug. Adverse events and SAEs must be reported up until 1) within 15 (\pm 2) days after the last application of study drug or 2) until toxicities resolve, return to baseline, stabilize, or are deemed irreversible, whichever is longer. Reasonable efforts should be made to have the participant return for the follow-up visit and report any AEs that may occur during this period.

9. ADVERSE EVENTS: DEFINITIONS AND PROCEDURES FOR RECORDING, EVALUATING, FOLLOW-UP, AND REPORTING

9.1. Definition of Adverse Event

Adverse Event Definition

• An AE is any untoward medical occurrence associated with the use of a drug in humans, whether or not it is considered drug-related.• An AE can therefore be any unfavorable or unintended sign (including an abnormal laboratory finding), symptom, or disease (new or exacerbated) temporally associated with the use of study drug.
Additional Guidance for Events Meeting the Adverse Event Definition

• Any safety assessments (eg, vital signs measurements), including those that worsen from baseline, considered clinically significant in the medical and scientific judgment of the investigator (ie, not related to progression of underlying disease) are to be reported as an AE.• Abnormal laboratory test results are to be reported as an AE if they are considered clinically meaningful, induce clinical signs or symptoms, require concomitant therapy, or require changes in study drug. Whenever possible, a diagnosis (eg, anemia, thrombocytopenia) should be recorded in the eCRF rather than the abnormal laboratory test result (eg, low hemoglobin, platelet count decreased).• Exacerbation of a chronic or intermittent pre-existing condition/disease, including either an increase in the frequency and/or intensity of the condition, is to be reported as an AE.• New conditions detected or diagnosed after the start of study drug administration are to be reported as an AE.• Signs, symptoms, or the clinical sequelae of a suspected drug-drug interaction are to be reported as an AE.• Signs and/or symptoms from dosing errors of a study drug (eg, overdose) or a concomitant medication are to be reported as an AE.• "Lack of efficacy," "disease progression," or "failure of expected pharmacological action" will not be reported as an AE or SAE. Such instances will be captured in the efficacy assessments.• A condition that leads to a medical or surgical procedure (eg, endoscopy, appendectomy) will be reported as an AE if it occurs after obtaining informed consent. If the condition is present before entering the study, then it should be captured as medical history.• Pre-existing diseases or conditions with expected fluctuations in signs or symptoms should be reported as an AE only if the investigator judges the fluctuation to have worsened more than expected during study participation.

9.2. Definition of Serious Adverse Event

If an event is not an AE per the definition above, then it cannot be an SAE even if serious conditions are met (eg, hospitalization for signs/symptoms of the disease under study, death due to progression of disease).

A serious adverse event is defined as any untoward medical occurrence that, at any dose:	
a. Results in death	
b. Is life-threatening	
The term "life-threatening" in the definition of "serious" refers to an adverse drug experience that places the participant, in the opinion of the initial reporter, at immediate risk of death from the adverse experience as it occurs. This does not include an adverse drug experience that, had it occurred in a more severe form, might have caused death.

c. Requires inpatient hospitalization or prolongation of existing hospitalization	
In general, hospitalization signifies that the participant has been detained (involving at least an overnight stay) at the hospital or emergency ward for observation and/or treatment that would not have been appropriate in the physician's office or outpatient setting. Complications that occur during hospitalization are AEs. If a complication prolongs hospitalization or fulfills any other serious criteria, the event is serious. When in doubt as to whether hospitalization occurred or was necessary, the AE should be considered serious.
 
Hospitalization for elective treatment or planned surgery (eg, stent replacement, hip surgery) is not considered an SAE.
 
Hospitalization for medical interventions in which no unfavorable medical occurrence occurred (ie, elective procedures or routine medical visits) are not considered SAEs.

d. Results in persistent or significant disability/incapacity	
The term "disability" means a substantial disruption of a person's ability to conduct normal life functions. This definition is not intended to include experiences of relatively minor medical significance, such as uncomplicated headache, nausea, vomiting, diarrhea, influenza, and accidental trauma (eg, sprained ankle), that may interfere with or prevent everyday life functions but do not constitute a substantial disruption.

e. Is a congenital anomaly/birth defect	
f. Is an important medical event	
An important medical event is an event that may not result in death, be immediately life-threatening, or require hospitalization but may be considered serious when, based on appropriate medical judgment, the event may jeopardize the participant and may require medical or surgical intervention to prevent one of the outcomes listed in the above definition. Examples of such events include new invasive or malignant cancers, intensive treatment in an emergency department or at home for allergic bronchospasm, blood dyscrasias, or convulsions that do not result in hospitalization, or development of drug dependency or drug abuse.

9.3. Recording and Follow-Up of Adverse Events and/or Serious Adverse Events

Adverse Event and Serious Adverse Event Recording

- An AE/SAE (including local and systemic reactions) that begins or worsens after informed consent is signed should be recorded on the Adverse Event Form in the eCRF. AEs/SAEs should be reported for enrolled participants, but only SAEs need to be reported for screen failure participants. For enrolled participants, conditions that were present at the time informed consent was given should be recorded on the Medical History Form in the eCRF. For detailed information refer to the eCRF guidelines.
- When an AE/SAE occurs, it is the responsibility of the investigator to review all documentation (eg, hospital progress notes, laboratory reports, and diagnostic reports) related to the event.
- The investigator (or delegate) will then record all relevant AE/SAE information in the eCRF.
- It is **not** acceptable for the investigator to send photocopies of the participant's medical records in lieu of completing the Adverse Event Form in the eCRF.
- There may be rare instances when copies of medical records for certain cases are requested. In this case, all participant identifiers, with the exception of the participant number, will be redacted by the site staff on the copies of the medical records before submission. These records can be submitted to Incyte Pharmacovigilance by email/fax per the contact information listed in the SRM.
- The investigator will attempt to establish a diagnosis of the event based on signs, symptoms, and/or other clinical information. Whenever possible, the diagnosis (not the individual signs/symptoms) will be documented as the AE/SAE. When a clear diagnosis cannot be identified, each sign or symptom should be reported as a separate AE/SAE.

To the extent possible, each AE/SAE should be evaluated to determine the following:

- The severity grade (CTCAE v5.0 Grade 1 to 5). See below for further instructions on the assessment of severity.
- Whether there is at least a reasonable possibility that the AE is related to the study drug: suspected (yes) or not suspected (no). See below for further instructions on the assessment of causality.
- The start and end dates, unless unresolved at the final safety follow-up visit.
- The action taken with regard to study drug as a result of the AE/SAE(s).
- The event outcome (eg, not recovered/not resolved, recovered/resolved, recovering/resolving, recovered/resolved with sequelae, fatal, unknown).
- The seriousness, as per the SAE definition provided in Section 9.2.
- The action taken with regard to the event. Note: If an AE is treated with a concomitant medication or nondrug therapy, this action should be recorded on the Adverse Event Form and the treatment should be specified on the appropriate eCRF (eg, Prior/Concomitant Medications, Procedures and Non-Drug Therapy).

Assessment of Intensity

The severity of AEs/SAEs will be assessed using CTCAE v5.0 Grades 1 through 5. If an event is not classified by CTCAE, the severity of the AE will be graded according to the scale below to estimate the grade of severity. For grading of AEs related to laboratory values; the CTCAE grading of the laboratory result should generally be followed (eg, for an AE of thrombocytopenia, the CTCAE grading of platelet count decreased should be followed).

The investigator will make an assessment of intensity for each AE and SAE reported during the study and assign it to 1 of the following categories:

- **Grade 1:** Mild; asymptomatic or mild symptoms; clinical or diagnostic observations only; treatment not indicated.
- **Grade 2:** Moderate; minimal, local, or noninvasive treatment indicated; limiting age-appropriate activities of daily living.
- **Grade 3:** Severe or medically significant but not immediately life-threatening; hospitalization or prolongation of hospitalization indicated; disabling; limiting self-care activities of daily living.
- **Grade 4:** Life-threatening consequences; urgent treatment indicated.
- **Grade 5:** Fatal.

Assessment of Causality

- The investigator is obligated to assess the relationship between study drug and each occurrence of each AE/SAE.
- A "reasonable possibility" of a relationship conveys that there are medical facts, evidence, and/or arguments to suggest a causal relationship, rather than that a relationship cannot be ruled out.
- The investigator will use clinical judgment to determine the possibility of a relationship.
- The investigator will also consult the RSI in the IB in making his/her assessment.
- Alternative causes, such as underlying or concurrent disease(s), concomitant therapy, and other risk factors, as well as the temporal relationship of the event to study drug administration, will be considered and investigated.
- For each AE/SAE, the investigator **must** document in the medical notes that he/she has reviewed the AE/SAE and has provided an assessment of causality.
- With regard to assessing causality of SAEs:
 - There may be situations in which an SAE has occurred and the investigator has minimal information to include in the initial report. However, the causality assessment is one of the criteria used when determining regulatory reporting requirements. **Therefore, it is very important that the investigator always make an assessment of causality based on the available information for every event before the initial transmission of the SAE.**
 - The investigator may change his/her opinion of causality in light of follow-up information and submit the updated causality assessment.

Follow-Up of Adverse Events and Serious Adverse Events

- The investigator is obligated to perform or arrange for the conduct of supplemental measurements and/or evaluations as medically indicated or as requested by the sponsor to elucidate the nature and/or causality of the AE or SAE as fully as possible. This may include additional laboratory tests or investigations, histopathological examinations, or consultation with other health care professionals.
- Once an AE is detected, it should be followed in the AE eCRFs until it has resolved, has stabilized, or until it is judged to be permanent; assessment should be made at each visit (or more frequently if necessary) of any changes in severity, the suspected relationship to the study drug, the interventions required to treat the event, and the outcome.
- When the severity of an AE changes over time for a reporting period (eg, between visits), each change in severity will be reported as a separate AE.
- If a participant dies during participation in the study or during a recognized follow-up period, the investigator will provide the sponsor with a copy of any postmortem findings, including histopathology.
- Updated SAE information will be recorded in the originally completed eCRF and reported to Incyte Pharmacovigilance until resolution, stabilization, the event is otherwise explained, or the participant is lost to follow-up.
- Any updated SAE data (including SAEs being downgraded to nonserious) will be submitted to the sponsor (or designee) within 24 hours of receipt of the information.

In the event a participant experiences a skin reaction and that an allergic contact dermatitis is suspected, the event should be documented as an AE, and patch testing may be performed to confirm the diagnosis.

